Safety analysis: To assess clinical safety, AEs, vital sign measurements and clinical laboratory information will be summarized. AEs will be coded using the Medical Dictionary for Regulatory Activities (MedDRA). Changes from baseline for clinical laboratory values and vital signs will be summarized over time. Descriptive statistics and shift tables will be generated as appropriate.

Efficacy/Pharmacodynamic Effects Analysis of Secondary Endpoints:

All efficacy analyses will be performed for the EE and mITT populations.

Efficacy will be evaluated by determining the proportion of patients who have a modified HI-E erythroid response rate based upon the IWG 2006 criteria ([Appendix 5](#)), defined as 1) A mean hemoglobin increase ≥ 1.5 g/dL over an 8-week period as compared to baseline, not influenced by RBC transfusion in NTD patients or 2) A decrease of ≥ 4 units or $\geq 50\%$ of units of RBCs transfused over a period of 8 weeks, relative to the number of units of RBCs transfused in the 8 weeks immediately prior to Cycle 1 Day 1 in TD patients.

Baseline hemoglobin will be the average of two or more measures (not influenced by RBC transfusion) performed during the screening period for study A536-03 (for patients without interruption) or study A536-05 (for patients with interruption).

Baseline units of RBCs transfused will be the 8-week period prior to study A536-03 (for patients without interruption) or study A536-05 (for patients with interruption).

The erythroid response will be summarized using both a point estimate and its exact 95% confidence interval based on binomial distribution.

No direct comparison testing with concurrent or historical controls will be performed.

Analysis of other Secondary efficacy/pharmacodynamic endpoints will include:

- Time to HI-E response and duration of HI-E response as per the IWG 2006 criteria and modified IWG 2006 criteria.
- Mean RBC transfusion burden
- Rate of RBC transfusion-free period lasting \geq 8 weeks in TD patients.
- Mean hemoglobin level change in NTD patients
- Other PD endpoints including:
 - Biomarkers for iron overload/metabolism
 - Relationship of biomarkers to response
 - Rates of HI-N and HI-P

The **exploratory endpoints** will include:

- Biomarkers related to the TGF- β superfamily.
- Patient-reported quality of life using tools including but not limited to the FACT-An questionnaire

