10.2.2. RBC Transfusions

Concurrent treatment for anemia with blood transfusions is allowed, at the discretion of the investigator, for low hemoglobin levels, symptoms associated with anemia (e.g., hemodynamic or pulmonary compromise requiring treatment) or comorbidity.

For any RBC transfusions (NTD or TD patients) received during the study, collect hemoglobin values just prior to transfusion.

Each TD patient will have a “pre-transfusion hemoglobin threshold” for requiring transfusion, which will be calculated based on transfusion history and will be used for determining when to transfuse during the study. The baseline pre-transfusion hemoglobin threshold will be the mean of all documented pre-transfusion hemoglobin values during the 12 weeks prior to C1D1 of base study A536-03 for patients without treatment interruption, or prior to C1D1 of study A536-05 for patients with treatment interruption. During treatment, if the pre-transfusion hemoglobin level is increased by ≥ 1 g/dL compared to the baseline pre-transfusion hemoglobin threshold for that patient, transfusion should be delayed by a minimum of 7 days and/or the number of units transfused should be reduced by 1 or more RBC units. Patients should not be transfused if hemoglobin is ≥ 9 g/dL unless indicated for symptoms related to anemia or other reasons at the investigator’s discretion.

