## 5. STATISTICAL METHODOLOGY

### 5.1. Definitions

#### Transfusion Status

For patients without treatment interruption, transfusion status (LTB or HTB) will carry-over from the base study A536-03. For patients with treatment interruption, transfusion status will be reassessed prior to C1D1 of study A536-05. Transfusion status for all patients is defined as follows for all patients:

- LTB patients are defined as patients who require a transfusion of < 4 units of RBCs in the 8 weeks prior to C1D1
- HTB patients are defined as patients who require a transfusion of  $\geq 4$  units of RBCs in the 8 weeks prior to C1D1

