## 5.8. Efficacy and Safety Analyses

No formal hypothesis testing is planned. All efficacy analyses will be performed using the ITT population.

In general, the below rules apply to the derivations of efficacy endpoints related to hemoglobin and RBC transfusion data unless specified otherwise:

- Hemoglobin measurements within 7 days following RBC transfusion will be excluded from the efficacy analysis
- For each patient, all efficacy endpoints will be derived based on an analysis cutoff day, defined as the last dose + 56 days or the last date from transfusion record data, whichever is earlier.

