### 5.8.2. Secondary Efficacy Endpoints

#### 5.8.2.1. Erythroid Response (modified HI-E from IWG 2006 criteria)

Erythroid response (modified HI-E from IWG 2006 criteria) is defined as the proportion of patients with:

- A mean hemoglobin (Hgb) increase  $\geq 1.5$  g/dL over an 8-week period as compared to baseline, not influenced by RBC transfusion, in LTB patients.
- A decrease of  $\geq 4$  units or  $\geq 50\%$  of units of RBCs transfused over a period of 8 weeks, relative to the 8 weeks immediately prior to Day 1, in HTB patients.

A point estimate of the proportion of patients achieving a modified erythroid response will be presented along with its associated exact 95% confidence interval based on binomial distribution.

The complete hemoglobin measurements and RBC transfusion records will be listed for each patient.

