#### 5.8.2.3. HI-E Response Rate

Erythroid (HI-E) response will be defined following IWG 2006 criteria.

- For low transfusion burden (LTB) patients, a hemoglobin increase of  $\geq 1.5$  g/dL from baseline during any rolling 8-week period in the absence of transfusion. The rolling 8-week period starts and ends at a hemoglobin measurement date with duration  $\geq 8$  weeks.

- For high transfusion burden (HTB) patients, a reduction by  $\geq 4$  RBC units transfused during any rolling 8-week interval on treatment compared to baseline.

A point estimate of the proportion of HI-E responders will be presented along with its associated exact 95% confidence interval based on binomial distribution. HI-E response will also be listed for each patient.

There are two versions of a HI-E response for LTB patients.

- All hemoglobin values increase of  $\geq 1.5$  g/dL from baseline during any rolling 8-week period in the absence of transfusion.
- Mean hemoglobin value increase of  $\geq 1.5$  g/dL from baseline during any rolling 8-week period in the absence of transfusion.

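### Modified HI-E in low-transfusion-burden patients guards against transfusion only by a 7-day exclusion of hemoglobin values, whereas the SAP's IWG HI-E for the same patients requires a transfusion-free window

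*Protocol*

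**What the plan says.** The protocol (synopsis and Section 15.2.3) counts an NTD patient as a modified HI-E responder on "A mean hemoglobin increase ≥ 1.5 g/dL over an 8-week period as compared to baseline, not influenced by RBC transfusion in NTD patients". It does not say what makes a value, or a period, free of transfusion influence. SAP 5.8.2.1 keeps the wording: a mean rise of at least 1.5 g/dL "over an 8-week period as compared to baseline, not influenced by RBC transfusion, in LTB patients".

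The operational rule is in SAP 5.8 and applies to hemoglobin endpoints unless another section overrides it: "Hemoglobin measurements within 7 days following RBC transfusion will be excluded from the efficacy analysis". SAP 5.1 uses the same 7-day rule for baseline hemoglobin. SAP 5.13, describing the protocol's baseline definition, also ties transfusion influence to a 7-day interval.

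SAP 5.8.2.3 is stricter for IWG HI-E in the same patients. The rise must be "from baseline during any rolling 8-week period in the absence of transfusion", in both an all-values and a mean-value version.

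On who can be transfused, SAP 5.1 states: "LTB patients are defined as patients who require a transfusion of < 4 units of RBCs in the 8 weeks prior to C1D1". Up to 3 units before entry are therefore compatible with LTB status. Protocol 10.2.2 adds: "Concurrent treatment for anemia with blood transfusions is allowed, at the discretion of the investigator". That section gives an individual pre-transfusion threshold to TD patients only, and asks for a hemoglobin value just before every transfusion in NTD and TD patients alike.

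**The concern.** Transfused cells circulate for much longer than 7 days. Dropping the first week of values does not make the rest of the window independent of the transfusion. Nothing in SAP 5.8 or 5.8.2.1 requires the 8 weeks to be transfusion-free, limits on-study units for LTB patients, or makes a transfused LTB patient a non-responder.

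The patient at issue is one whose transfusion need rises after entry. The added units can lift mean hemoglobin above baseline, and the patient is then scored as responding to the drug. Other planned summaries only partly offset this: the transfusion-burden summaries in SAP 5.8.2.10 cover HTB patients, and RBC transfusion independence in 5.8.2.2 covers patients with at least 2 units at baseline. With no control arm, any misclassification passes straight into the reported proportion and its exact confidence interval.

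**Working it through.** The documents state no figure for this endpoint to reproduce, so the check has a part that uses document inputs only and a part that rests on stated assumptions.

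**1. How much the 7-day rule removes (documents only).** Inputs: 8-week window (56 days); exclusion 7 days (SAP 5.8); dosing visits 21 ± 5 days apart (Protocol Section 2, note 2).

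- Share of the window masked by one transfusion: 7/56 = 12.5%.
- A transfusion d days after a visit leaves the next scheduled value in the analysis when (interval − d) > 7. Counting d from 0 to interval − 1 gives 14 of 21 days (67%) at 21 days, 9 of 16 (56%) at 16 days and 19 of 26 (73%) at 26 days.
- A transfusion given after the blood sample at each visit removes no scheduled value.

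**2. What the retained values carry (assumed kinetics).** Assume that each unit adds g = 0.7 to 1.0 g/dL, lost linearly over L = 60 to 100 days. The share left after d days is 1 − d/L. For L = 60 this is 0.87 at day 8 and 0.65 at day 21; for L = 100 it is 0.92 and 0.79.

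**3. Chance of a false response in one window (assumed).** Simulated: no drug effect; 2 units every 28 days, that is 4 units in 56 days, which equals the TD threshold; random timing; within-patient SD 0.5 g/dL; untransfused two-value baseline; visits every 21 days; values within 7 days after a transfusion removed. The result is the probability that the retained mean is at least 1.5 g/dL above baseline, without and with the pre-transfusion values that Protocol 10.2.2 requires.

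| g, L | Own Hgb unchanged: visits only | plus pre-transfusion values | Own Hgb down 1 g/dL: visits only | plus pre-transfusion values |
|---|---|---|---|---|
| 0.7, 60 | 0.37 | 0.18 | 0.01 | 0.00 |
| 1.0, 60 | 0.77 | 0.56 | 0.13 | 0.02 |
| 0.7, 100 | 0.95 | 0.91 | 0.35 | 0.18 |
| 1.0, 100 | 1.00 | 1.00 | 0.94 | 0.87 |

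Pre-transfusion values are troughs and nothing in SAP 5.8 removes them, so the columns that include them are the ones to use.

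**4. Effect of transfusion at baseline (assumed).** A grid without random error: g = 0.7 or 1.0; L = 60, 80 or 100; 0, 2 or 3 units given on day −35; 1 or 2 units every 21 days on study, given after the visit sample; best mean of four consecutive visit values. Combinations reaching a rise of 1.5 g/dL with no drug effect:

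| Baseline units | 1 unit per 21 days | 2 units per 21 days |
|---|---|---|
| 0 | 1 of 6 | 5 of 6 |
| 2 | 0 of 6 | 3 of 6 |
| 3 | 0 of 6 | 1 of 6 |

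In total 10 of 36 qualify. All 10 would be non-responders if the window had to be transfusion-free.

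**The case against.** Four points can be made against the concern.

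- *The clean analysis is already planned.* The mean-value version in SAP 5.8.2.3 is close to the LTB criterion that the fix would produce, and full hemoglobin and transfusion records are to be listed per patient. This stands. A reader might infer that the trial will report no transfusion-free mean response; that is not so. What remains is that the first-listed efficacy endpoint is the more lenient of the two, and the list of changes in SAP 5.13 gives no reason.
- *The high probabilities need implausible transfusion.* This largely stands. With 2 units every 28 days, the steady-state rise just before a transfusion is 2g × Σ(1 − 28k/L) over the positive terms. For g = 1.0 and L = 100 that is 2 × (0.72 + 0.44 + 0.16) = 2.64 g/dL above baseline. Protocol 10.2.2 says patients should not be transfused at 9 g/dL or above, although the sentence sits in the TD paragraph and allows discretion. Staying below 9 would need a baseline below 9 − 2.64 = 6.36 g/dL, or below 7.36 with a 1 g/dL fall. NTD patients who become transfusion dependent may also be taken off treatment for lack of effect (Protocol 9.3).
- *Baseline carries the same contamination.* This stands. Baseline uses the same 7-day rule, so the bias needs more transfusion on study than before it, as the grid shows.
- *Little depends on this rate.* Also true. There is no primary efficacy endpoint, no hypothesis test and no control comparison, so no error rate is affected.

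Two stronger readings are tempting. One is that the response rate is inflated by something like the simulated percentages. Those apply to one hypothetical patient in one window; the documents give no count of such patients. The other is that the protocol itself adopts the 7-day rule for response. The protocol leaves its phrase undefined. A stricter program would be compatible with it, but no document specifies one.

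**Conclusion.** The concern holds in a limited form. As written, SAP 5.8 and 5.8.2.1 allow an LTB patient transfused more on study than at baseline to count as a modified HI-E responder, while 5.8.2.3 rules this out for IWG HI-E. The defect touches the modified HI-E rate and the maximum 8-week mean hemoglobin change in LTB patients (5.8.2.10), both descriptive.

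That 56% to 73% of transfusion days leave the next scheduled value in place follows from the documents alone. The per-window chance of a false response, 18% to 100%, or 0% to 87% after a 1 g/dL fall in the patient's own hemoglobin, rests on assumed kinetics, an untransfused baseline and 2 units every 28 days. The top of each range is unlikely. The direction is upward for patients whose transfusion rises; the size of the effect on the trial's rate cannot be computed. This is a cheap improvement, not a flaw that undermines the study.

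**What to change.** In SAP 5.8.2.1, require the LTB 8-week period to contain no RBC transfusion, as 5.8.2.3 does, and continue to exclude values within 7 days after a transfusion given before the period began. Apply the same condition to the maximum 8-week mean hemoglobin change in 5.8.2.10. Report the 7-day-exclusion version as a sensitivity analysis, so that the difference between the two shows how many responders depend on transfusion. If this is already the intention, one sentence saying so before database lock is enough.

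The cost is one phrase and one programming condition on data already collected. The LTB modified HI-E rate may be slightly lower, and its LTB part will nearly duplicate the mean-value HI-E version.

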2. SCHEDULE OF EVENTS

	Screening ¹	Cycle 1	Cycle 2	Cycle 3	Cycle 4	Cycle 5	Cycle 6	Cycle 7	Cycle 8	Cycle 9
		C1D1 ²	C2D1 ²	C3D1 ²	C4D1 ²	C5D1 ²	C6D1 ²	C7D1 ²	C8D1 ²	C9D1 ²
Informed consent	X ¹									
Inclusion/Exclusion	X	X ²								
Medical history ³	X									
QoL Questionnaires ⁴		X				X				X
Physical examination	X	X				X				X
Vital signs ⁵	X	X	X	X	X	X	X	X	X	X
ECOG Status	X	X		X		X		X		X
ECG (12 lead) ⁶		X								
Bone marrow aspirate ⁷	X	X ⁷								X ⁷
Serum iron studies ⁸		X				X				X
Erythropoietin levels		X				X				X
Hematology ⁹	X	X	X	X	X	X	X	X	X	X
Peripheral blood smear		X				X				X
Serum chemistry ¹⁰	X	X		X		X		X		X
Urinalysis and Urine Chemistry ¹¹	X	X				X				X
Anti-Drug Antibody ¹²		X				X				X
PK collection		X				X				X
PD biomarkers ¹³		X				X				X
Pregnancy test ¹⁴	X	X	X	X	X	X	X	X	X	X
Evaluate transfusion frequency ¹⁵	X	X	X	X	X	X	X	X	X	X
Administer ACE-536		X	X	X	X	X	X	X	X	X
Concomitant medications and AEs	Collected Continuously									

	Cycle 10	Cycle 11	Cycle 12	Cycle 13	Cycle 14	Cycle 15	Cycles 16 - 87 ^{2,16}	EOT ¹⁷	PTFU ¹⁸	LTFU ¹⁹	EOS ²⁰
	C10D1 ²	C11D1 ²	C12D1 ²	C13D1 ²	C14D1 ²	C15D1 ²					
Informed consent											
Inclusion/Exclusion											
Medical history ³											
QoL Questionnaire ⁴					(X) ⁴			X			
Physical examination					X			X			
Vital signs ⁵	X	X	X	X	X	X		X			
ECOG Status		X		X		X		X			
ECG (12 lead) ⁶								X			
Bone marrow aspirate ⁷					(X) ⁷			X ⁷			
Serum iron studies ⁸					X			X	X		
Erythropoietin levels					X			X	X		
Hematology ⁹	X	X	X	X	X	X		X	X		
Peripheral blood smear					X			X			
Serum chemistry ¹⁰		X		X		X		X			
Urinalysis and Urine Chemistry ¹¹					X			X			
Anti-Drug Antibody ¹²					X			X ¹²			
PK Collection					X			X			
PD biomarkers ¹³					X			X			
Pregnancy test ¹⁴	X	X	X	X	X	X		X			
Evaluate transfusion frequency ¹⁵	X	X	X	X	X	X		X	X		
Administer ACE-536 ²	X	X	X	X	X	X					
Monitoring for AEs of special interest ²¹ (Refer to Section 14.1 for details)	After signing ICF and until at least 3 years post last dose of IP or until death, loss to follow up, withdrawal of consent for further data collection.										
Survival follow-up ²¹										X	X
Concomitant medications and AEs	Collected Continuously										

- ¹ **Screening procedures:** Other than informed consent, procedures listed as part of the 28-day screening period are only applicable to patients with treatment interruption. Patients with treatment interruption will need to qualify per the additional inclusion criteria listed in [Section 9.2.1](#). For patients without treatment interruption, C1D1 may coincide with EOT visit of the base study A536-03. Procedures that are required to confirm eligibility for patients without treatment interruption can be performed at the base study A536-03 EOT visit and used to confirm eligibility prior to dosing on C1D1 of study A536-05.
- ² **Study procedures** must be done prior to administration of study drug. For patients without treatment interruption, C1D1 procedures shaded grey may be conducted as part of the EOT visit for study A536-03 and may not need to be repeated for study A536-05. All screening and Cycle 1 Day 1 procedure results required to confirm eligibility must be obtained and reviewed prior to study drug administration in A536-05.
Visit schedule: Each dosing visit (cycles 1-87) will be 21 days (\pm 5 days) from the previous dosing visit, unless a dose delay is required. If a dose delay is required per the dose modification rules ([Section 10.8](#)), the patient will not be dosed. The patient will return every 1-3 weeks for assessment of hematology results and AEs until the patient is eligible to receive the next dose of ACE-536 and start the next cycle. The patient should resume the study at the planned dosing cycle (e.g. if the patient missed a dose at C4D1, then they would resume dosing at C4D1 and not skip to C5D1).
Dosing: The patient dose must be calculated based on the patient's weight on the day of dosing. Dose modification rules and titration rules must be reviewed and implemented prior to dosing as required per protocol (see [Section 10.8](#) and [Section 10.9](#)). A dose titration cannot occur until C3D1.
- ³ **Medical History:** Medical history for patients with treatment interruption will include medical events occurring after EOS visit in study A536-03 and prior to C1D1 for study A536-05. Medical history for patients without treatment interruption will be taken from study A536-03.
- ⁴ **Quality of life questionnaires** are only required on C1D1, C5D1, C9D1, C13D1, C17D1, C25D1, C33D1, C41D1, C49D1, C57D1, C65D1, C73D1, C81D1, EOT, and EOS.
- ⁵ **Vital signs** will include weight, heart rate, and systolic and diastolic blood pressure.
- ⁶ **ECG:** May be collected within 28 days prior to C1D1.
- ⁷ **Bone marrow aspirate:** Patients with treatment interruption must have a bone marrow aspirate including cytogenetics performed \leq 3 months prior to C1D1 for evaluation of eligibility per inclusion criteria [Section 9.2.1](#). A bone marrow aspirate will not be performed on C1D1 for patients without treatment interruption. A bone marrow aspirate must be performed within 21 days after C9D1, C17D1, C25D1, C41D1, C57D1, and C73D1 for all patients. At the EOT visit, a bone marrow aspirate is required for all patients, unless performed $<$ 3 months following a previous bone marrow aspirate and not clinically indicated. Refer to the Laboratory Manual for processing and shipping instructions.
- ⁸ **Serum Iron Studies:** May include serum iron, TIBC, transferrin, soluble transferrin receptor, ferritin.
- ⁹ **Hematology:** RBC, WBC with differential, hemoglobin, hematocrit, nucleated red blood cells (nRBC), reticulocyte count, platelet count, peripheral blasts, mean corpuscular volume (MCV), mean corpuscular hemoglobin (MCH), mean corpuscular hemoglobin concentration (MCHC), and red blood cell distribution width (RDW). On dosing days, hemoglobin values may be drawn and resulted (up to 1 day) prior to dosing (see [Section 10.8](#), Individual Dose Modification Rules).
- ¹⁰ **Serum Chemistry:** Sodium, potassium, AST, ALT, lactate dehydrogenase (LDH), total bilirubin, direct bilirubin, alkaline phosphatase, blood urea nitrogen (BUN)/urea, creatinine, gamma-glutamyl transpeptidase (GGT), calcium, phosphorus, glucose, amylase, lipase, total protein, albumin, and uric acid.
- ¹¹ **Urinalysis by dipstick analysis (local lab):** pH, specific gravity, protein, glucose, ketones, blood, leukocyte esterase, and nitrite, with microscopic examination if indicated. **Urine Chemistry (central lab):** urine chemistries include but are not limited to: microalbumin and creatinine.
- ¹² If the patient has a **positive ADA** result at their last assessment, the patient may be asked to return approximately every three months for additional testing, until a negative result is obtained or the result is considered stabilized.
- ¹³ **PD Biomarkers:** May include hepcidin, GDF15, GDF8, GDF11, Activin A and others to be determined.
- ¹⁴ **Pregnancy test:** (urine or serum) is required for female patients of child bearing potential only.
- ¹⁵ **Transfusion Frequency:** Transfusion history will be collected from the EOS visit in the base study A536-03 through the C1D1 visit of A536-05 as available for patients with treatment interruption up to 24 weeks. TD patients will have a defined "pre-transfusion hemoglobin threshold" for requiring transfusion during the study which will be calculated based on transfusion history and will be used for determining when to transfuse during the study. The baseline pre-transfusion hemoglobin threshold will be the mean of all documented pre-transfusion hemoglobin values during the 12 weeks prior to C1D1 of base study A536-03 (for TD patients without treatment interruption) or study A536-05 (for TD patients with treatment interruption). During treatment, if the

pre-transfusion hemoglobin level is increased by ≥ 1 g/dL compared to the baseline pre-transfusion hemoglobin threshold for that patient, transfusion should be delayed by a minimum of 7 days and/or the number of units transfused should be reduced by 1 or more RBC units. Patients should not be transfused if hemoglobin is ≥ 9 g/dL unless indicated for symptoms related to anemia or other reasons at the investigator's discretion.

- ¹⁶ **Cycles 16 through 87:** Patients may complete up to 87 Cycles. The last dose of ACE-536 may not be administered after 87 cycles or 1825 calendar days from C1D1, whichever occurs first.
- ¹⁷ **End of Treatment (EOT):** Should be performed 28 days (± 7 days) after the last dose of ACE-536. Patients who discontinue treatment early should complete the EOT visit at the time of discontinuation, followed by PTFU, LTFU, and EOS visits.
- ¹⁸ **Post-Treatment Follow-Up (PTFU):** Patients will complete the PTFU visit 2 months (± 7 days) after the last dose of ACE-536
- ¹⁹ **Long-Term Follow-Up (LTFU):** Patients will complete LTFU visits every 3 months (± 7 days) after the last dose of ACE-536 for 3 years after the last dose of ACE-536.
- ²⁰ **End of Study (EOS):** Should be performed 3 years after the last dose of ACE-536.
- ²¹ Long-Term Post-Treatment Follow-Up for overall survival (OS), progression to AML, other malignancies/pre-malignancies (please refer to [Section 14.1](#) for details) may be conducted by record review (including public records if allowed by local regulations) and/or telephone contact with the patient, family, or the patient's treating physician. The investigator must make every effort to obtain information regarding the patient's survival status before determining the patient is lost to follow-up.

